#### **A.3. Low levels of day-to-day reward may also be a relevant maintenance factor for mental health conditions characterized by compulsive engagement in or use of highly rewarding stimuli.**

There is a growing body of evidence to suggest that insufficient reward from day-to-day life activities is a relevant maintenance factor for many mental health conditions beyond depression. In particular, mental health conditions characterized by compulsive engagement in or use of highly rewarding stimuli despite adverse consequences (e.g. substance use disorder, behavioral addictions, eating disorders) appear to be maintained, in part, by insufficient reward from day-to-day life activities. When day-to-day life activities are not providing enough reward, these individuals may be more likely to seek out other stimuli that can immediately and powerfully activate neural reward pathways such as illicit substances or to over-indulge in naturally rewarding behaviors such as the consumption of palatable foods. A hyper-reward response (e.g. high activation of dopaminergic cortico-striatal reward pathways) to disorder specific stimuli (e.g. the feel of holding poker chips, the smell of highly palatable food, sexual imagery) may develop as individuals seek out larger quantities or more frequent exposure to a limited range of intensely stimulating sources of reward. We propose that these individuals may become stuck in a second vicious cycle (depicted in green text in Figure 1) whereby increasing reliance on one behavior/substance to provide reward further reduces the ability to experience reward from day-to-day life activities, which then subsequently drives continued engagement in highly rewarding but risky behaviors. Together, the blue and green pathways in Figure 1 comprise what we have termed a reward imbalance. While the reward imbalance is likely an important maintenance factor outside of the COVID-19 pandemic, the resulting disruptions to social networks are almost certainly exacerbating this cycle as depicted in Figure 1.

Figure 1

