## STATISTICAL DESIGN AND POWER

Descriptive statistics and exploratory graphing will be generated for all variables of interest measured at all time points (i.e., baseline, mid-treatment, post-treatment, 3-month follow-ups). Data summaries will be produced both for the combined sample, and separately by treatment condition. Variables will be transformed if necessary using Box-cox power transformation. Baseline characteristics will be compared between treatment conditions using ANOVA (or non-parametric Kruskal Wallis test, as appropriate) for continuous variables and a chi-square test for categorical variables. Key baseline variables that differ by condition will be considered for use as covariates in the analyses described below.

**Primary Aim 1.** To assess feasibility and acceptability, we will use the following benchmarks: (a) recruitment success: enrollment of 60 patients; (b) attrition: retention of >75% of patients through all assessments; (c) study retention: patients attend at least 90% of all treatment groups; (d) satisfaction: patients express high satisfaction with RRT based on feedback questionnaires.

**Primary Aim 2.** To evaluate the effect of each treatment condition on hypothesized targets, we will model the pattern of change in reward response to palatable food, reward response to day-to-day life activities, social isolation, and loneliness separately over time using multilevel models (PROC MIXED in SAS). The first level will model individual participant's score on the relevant target over time with baseline as time 0. At the second level, the individual intercept and slope will be entered as outcomes with treatment condition as a predictor. We will examine each treatment condition separately. The cross-level interaction between time and treatment condition will be used to determine the effect of treatment condition on the pattern of change in the hypothesized targets. Restricted maximum likelihood will be used to estimate model parameters and to test the significance of random effects. Both linear and higher-order time effects will be examined based on model selection criterion such as Akaike Information Criterion (AIC) and Bayesian Information Criterion (BIC). With the fitted multilevel model structure, statistical contrasts will be performed at mid-treatment, post-treatment, and 3-month follow-up.

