We will conduct mediation analysis to determine whether temporally-precedent changes in the hypothesized targets mediate differences in the primary outcomes between the two treatment conditions. In particular, we will examine improvement in each hypothesized target from baseline to mid-treatment assessment predicting post-treatment outcomes and improvement at post-treatment predicting 3-month follow-up outcomes. We will use the mediation model outlined by Preacher and Hayes to estimate the total and specific indirect effects of each hypothesized mediator individually. The bias-corrected bootstrap test will be applied to test the joint significance of the indirect pathways. This approach expands on Baron and Kenny's methods by providing additional guidelines and techniques that allow for the most robust and accurate interpretation of these mediating effects. Should these mediation analyses prove promising, we will explore how the entire pattern of changes in the mediators from baseline to later time periods (mid-treatment and post-treatment assessments) influences the corresponding pattern of outcomes over time using the parallel process growth models.

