**Primary Aim 3.** Analyses will be conducted via linear mixed effects models for longitudinal data, which increase power by fully exploiting the strong correlation in treatment outcomes of interests (i.e., percent binge frequency reduction and percent change in EDE global eating pathology) across time. Patterned covariance matrices as implemented in (PROC MIXED in SAS) and will be used to evaluate between group differences for percent binge reduction and percent change in EDE global eating pathology across the study as a whole, and at each assessment post-baseline. Separate variance components will be used to capture therapist and participant-within-therapist variation. The within-subject covariance matrix will be assumed common across study arms, with an exponential variance function to deal with heteroscedasticity and a continuous-time AR(1) correlation matrix to accommodate residual autocorrelation over the unequal-size time intervals between follow-ups. Outcomes at all four time points will be estimated jointly for maximum statistical efficiency in the presence of intermittent missingness and loss to follow-up. The model will include random effects for subject and time (with higher-order effects if needed to capture nonlinear change), and fixed effects for treatment arm, time by treatment interaction, demographic information, and baseline values of binge frequency and global eating pathology. Time-specific covariate-adjusted contrasts will be used to compare outcome between groups.

**Secondary Aim 1.** We will use the same analytic approach described above for Primary Aim 3 but will test the impact of treatment condition on secondary outcomes including depression, substance abuse, and quality of

life.

**Attrition.** Patterns of missing data will be examined. Likelihood-based estimation methods and multiple imputation models will be used to handle missing data. In addition, we will use Hedeker and Gibbons' procedure to examine if dropouts influence the multilevel model results. If the missingness mechanism is related to the missing outcome itself, we will use sensitivity analyses to explore how robust our findings are with respect to a range of assumptions regarding missing data.

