**Power analyses.** Using the method described by Raudenbush and implemented with the software Optimal Design, power calculations were made for mixed effects models. A sample size of 154 (77 for each condition) is required for 80% power to detect a medium effect with the significant level of 0.05 and four assessment points, assuming the ratio of the variability of level-1 coefficient to the variability of level-1 residual is one. Fritz and MacKinnon documented sample size requirements to guarantee 80% power at the significance level of 0.05 for mediation models. Under the assumption of a medium effect for intervention with the mediator and a medium effect for the mediator on outcome controlled for intervention, the required sample size is 72 in total with 36 per intervention arm to achieve 80% power in simple mediation models. Given our relatively small sample size ( $n=60$ ), our study is powered to detect large effect sizes. While we observed large effect sizes in our pilot trial of RRT compared to a wait list control, we anticipate that the effect sizes may be smaller in the current trial as supportive therapy is an active treatment condition. It is likely that we may be underpowered for formal tests of statistical significance in this preliminary study. We will rely on effect sizes for interpretation when underpowered.

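### The mediation analysis makes no provision for the outcome at the mediator's visit, so for the two reward targets symptom change over the same weeks can produce an indirect effect without mediation

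*SAP*

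**What the plan says.** The mediation plan is the second paragraph under Primary Aim 2 in the SAP. For the first lag, "we will examine improvement in each hypothesized target from baseline to mid-treatment assessment predicting post-treatment outcomes"; for the second, improvement at post-treatment predicts the 3-month outcome. The Preacher-Hayes model is used "to estimate the total and specific indirect effects of each hypothesized mediator individually", with a bias-corrected bootstrap. No covariates are listed.

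The only general covariate rule is in the opening paragraph of the SAP: "Key baseline variables that differ by condition will be considered for use as covariates in the analyses described below". It covers baseline variables only. The baseline binge frequency and eating pathology terms under Primary Aim 3 belong to that aim's model.

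The same-visit outcome will exist. Protocol D.6 schedules assessments at baseline, mid-treatment, post-treatment and 3 months, and the SAP says under Primary Aim 3: "Outcomes at all four time points will be estimated jointly for maximum statistical efficiency".

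A further model is conditional: "Should these mediation analyses prove promising, we will explore how the entire pattern of changes in the mediators" by parallel process growth models. Under Power analyses the SAP adds: "We will rely on effect sizes for interpretation when underpowered".

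**The concern.** Randomization protects the path from treatment to target. It does not protect the path from target to later outcome, where a common cause at the mediator's visit confounds the estimate. The obvious candidate is the symptom level at that visit, since the SAP itself calls the outcomes strongly correlated over time.

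The protocol supplies the missing link for both reward targets. On day-to-day reward, A.3 proposes that "increasing reliance on one behavior/substance to provide reward further reduces the ability to experience reward from day-to-day life activities". On palatable food, it says that an exaggerated reward response to disorder-specific stimuli "may develop as individuals seek out larger quantities or more frequent exposure to a limited range of intensely stimulating sources of reward". Treatment need not act on symptoms first: A.5 describes RRT as working directly on reward, which is enough to supply the treatment-to-target path.

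At stake is the reading of mechanism. A biased indirect effect could be reported as RRT working through reward when the data do not separate that from symptoms driving reward. Relying on effect sizes does not help, because the effect size itself is biased.

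**Working it through.** **The plan's own figure.** The SAP gives 72 participants for 80% power in a simple mediation model with medium paths, without defining medium numerically. Assuming standardized paths of 0.39, simulated power at 72 is 0.787-0.798 by joint significance and 0.835-0.857 by bias-corrected bootstrap. The figure reproduces. It concerns power when mediation is real, and says nothing about a false indirect effect.

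**Model with no true mediation.** All path values are assumptions. With x = arm, y = symptoms, m = target, visits 0, 1, 2, and unit variances within arm:

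- y1 = 0.5·y0 − d·x + e1
- m1 = 0.5·m0 + c·(y1 − 0.5·y0) − a·x + e2
- y2 = 0.7·y1 + e3
- mediator = m1 − m0; ρ = corr(y0, m0), 0 to 0.3

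Here c is the symptom-to-target link (0.3-0.5), a the direct treatment effect on the target (0 or 0.5 SD), and d the treatment effect on symptoms at the mediator's visit (0.3-0.8 SD). The target never affects y2. The treatment-to-mediator path is −(a + c·d) and the total effect is −0.7·d. The false share is the indirect effect divided by the total effect.

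**Plan as written (arm only).** The mediator's variance within arm is 1.

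- Level outcome: path from mediator to outcome = 0.525c − 0.175ρ; share = (c + a/d)(0.75c − 0.25ρ). Lowest at a = 0: 0.3 × (0.225 − 0.075) = 4.5%. Highest at a = 0.5: (0.5 + 0.5/0.3) × 0.375 = 81%.
- Change score y2 − y0, a proxy for the percent change named under Primary Aim 3: path = 0.525c + 0.325ρ; share = (c + a/d)(0.525c + 0.325ρ)/0.7. Highest at a = 0: 0.5 × 0.36/0.7 = 26%. Highest at a = 0.5: 2.167 × 0.36/0.7 = 111%.

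**With baseline target and outcome.** The mediator-to-outcome path is 0.7c, so share = c² + c·a/d under either scoring. Example with c = 0.3, a = d = 0.5: 0.09 + 0.30 = 39%.

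**With the same-visit outcome added to the outcome equation.** y2 depends only on y1, so the mediator-to-outcome path is 0. If y1 is measured with reliability 0.8, share = (c + a/d)·0.25c/(1 − 0.75c²), which is 2%-33%.

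| Model | a = 0 | a = 0.5 SD |
|---|---|---|
| Arm only, level outcome | 5%-19% | 14%-81% |
| Arm only, change score | 7%-26% | 21%-111% |
| Baselines added | 9%-25% | 28%-108% |
| Baselines and same-visit outcome | 0% | 0% |

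**No effect on symptoms (d = 0, a = 0.5).** A share is undefined. The false indirect effect under arm only is 0.5 × (0.525c − 0.175ρ) = 0.05-0.13 SD for a level outcome and 0.5 × (0.525c + 0.325ρ) = 0.08-0.18 SD for a change score.

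**Weak or absent link.** With baselines, c = 0.1 gives 1%-18% (0.01 up to 0.01 + 0.1 × 0.5/0.3) and c = 0 gives 0%. With arm only, c = 0, a = 0.5, d = 0.3 and ρ = 0.3, the share is still −12.5% (level) or +23% (change), which is one reason to include baselines.

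**How often a false effect is declared.** Bias-corrected bootstrap, n = 60, level outcome, ρ = 0.3, 1,000 trials of 500 draws per scenario:

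| Scenario | Arm only | Baselines | Same-visit outcome added |
|---|---|---|---|
| a = 0 | 2.8%-19.5% | 4.8%-37.7% | 0.8%-5.2% |
| a = 0.5 | 13.9%-42.0% | 34.0%-74.3% | 6.7%-9.2% |
| d = 0, a = 0.5 | 11.0%-22.9% | 26.7%-47.5% | 5.8%-6.6% |

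A second simulation with no direct treatment effect on the target (outcome correlation 0.6, baseline correlation 0.4) gave lower arm-only rates: 0.9%-3.7% at a link of 0.3 and 8.2%-13.3% at 0.5. At n = 600 (link 0.5, d = 0.5) the rates for the three models were 92%, 98% and 7%. This is bias, and a larger sample does not cure it.

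**The case against.** The strongest case against has five parts.

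- **The theory is hedged.** A.3 proposes a cycle that maintains or develops a disorder and gives no rate over about five weeks. This stands: the documents make the reverse path plausible without showing its strength, and the claim is limited to what can happen.
- **The largest figures need an assumed 0.5 SD direct effect on the target that does nothing to symptoms.** The SAP expects smaller effects against an active control. This also stands, which is why the a = 0 results are shown beside them.
- **Baseline adjustment can enlarge the bias.** True for some scorings only. At ρ = 0.3, c = 0.3, a = 0.5, d = 0.3, a change score gives 72% with arm only and 59% with baselines; a level outcome goes the other way.
- **The adjusted estimate cannot settle direction.** If mediation is real but complete by the mediator's visit, adjustment removes it. This stands and shapes the fix.
- **The growth models might catch the problem.** A false indirect effect would look promising and so trigger them. But the SAP does not describe them as addressing same-period symptom change.

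Three stronger readings are tempting, and the documents do not support them. One is that time order fails. With weekly sessions (Protocol D.2), sessions 5 and 10 are about 35 days apart, so a 28-day recall window opens about 7 days after session 5; the target change does come first. Another is that social isolation and loneliness share the problem. The same covariate is absent for them, but the readable text states no path from symptoms to those targets (Figure 1 is not shown). The third is that the target-engagement or efficacy conclusions are compromised; they come from separate models.

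**Conclusion.** The concern holds for both lags and for the two reward targets. Followed as written, the mediation analysis can return an indirect effect where there is none. Three conditions are needed: symptoms affect the reward target within the same weeks, treatment moves the target (directly or through symptoms), and the outcome carries forward to the next visit. The documents propose or state each of these in words but give no values, so the sizes above are illustrations over assumed ranges and not predictions for this trial.

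The consequence is limited to how the mediation result may be read. It matters because effect sizes will be interpreted even without significance, and because Protocol A.6 wants this pilot to inform whether a fully powered trial is worthwhile. The change should be made; it is not a condition for the trial's listed aims. Confidence is medium.

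**What to change.** For both lags:

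1. State whether the outcome is scored as a level or as percent change.
2. Put baseline target and baseline outcome in both the mediator and the outcome equations. With arm only and ρ = 0.3, true mediation of 100% is estimated as 50%-65% for a level outcome and 94%-121% for a change score; with baselines it is 100%.
3. Report the indirect effect with its interval side by side, (1) without and (2) with the outcome at the mediator's visit, entered in the outcome equation only: mid-treatment for the post-treatment outcome, post-treatment for the 3-month outcome.
4. State that (1) is biased if symptoms drive the target, and that (2) removes genuine mediation already complete by that visit, has low power at n = 60, and retains some bias if the same-visit outcome is measured with error.
5. Do not gate on significance. Unless the indirect effect persists in (2), describe the result as an association that does not separate target-driven from symptom-driven change.

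The cost is one more estimate per target, outcome and lag, from data already collected; the second is less precise and usually less favourable. Under assumed true mediation complete by the mediator's visit, detection at n = 60 falls from 27.5%-72% (baselines) to 4.9%-10.9% (same-visit outcome added). With a further later effect of 0.15 it falls from 53%-94% to 20.5%-35%. The adjusted share is then 0.15/(0.7·b1 + 0.15), where b1 is the target's effect on the same-visit outcome: 42% for b1 = 0.3 and 30% for b1 = 0.5, against a true 100%. This loss is why the adjusted estimate should sit beside the other and not replace it.

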## **A.7. Current study and specific aims.**

In the current study, we will revise our existing 10-session group RRT treatment manual to specifically address the challenges in building social support and enhancing both momentary and sustained reward during the COVID-19 pandemic (Preliminary Aim 1). In months 2-18, we will conduct a small pilot RCT that will randomize individuals to receive either 10-sessions of RRT (n=30) or supportive therapy (n=30), both delivered as group-treatments via videoconferencing software. The specific aims of the current study are to confirm the feasibility and acceptability of RRT for EDs (Primary Aim 1), evaluate the ability of RRT to engage critical targets including reward to day-to-day life activities, reward to palatable foods, social isolation, and loneliness (Primary Aim 2), and provide preliminary estimates of efficacy in reducing ED symptoms at both post-treatment and a 3-month follow-up (Primary Aim 3). We will also evaluate the impact of RRT on secondary outcome variables including depression, substance use, and quality of life (Secondary Aim 1).

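### With 60 patients, the bias-corrected bootstrap for mediation can reject at about 7% to 9% instead of 5% when exactly one path is null and the other is medium to large

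*SAP*

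**What the plan says.** The mediation analysis is described under Primary Aim 2 of the SAP. Each target is taken alone, with a model used "to estimate the total and specific indirect effects of each hypothesized mediator individually". Early change in a target is set against post-treatment outcomes, and change by post-treatment against 3-month outcomes. The test is fixed in one sentence: "The bias-corrected bootstrap test will be applied to test the joint significance of the indirect pathways". The SAP adds that the approach will "allow for the most robust and accurate interpretation of these mediating effects". It gives no number of resamples, no alternative interval and no sensitivity analysis for this test.

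The power section cites a source that "documented sample size requirements to guarantee 80% power at the significance level of 0.05 for mediation models". It assumes "a medium effect for intervention with the mediator and a medium effect for the mediator on outcome controlled for intervention" and concludes that "the required sample size is 72 in total with 36 per intervention arm to achieve 80% power in simple mediation models". The trial has 60 patients, 30 per arm (Protocol A.7). The same section concedes that formal tests may lack power and says that effect sizes will then carry the interpretation.

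**The concern.** An indirect effect is the product of two paths: treatment to target (a) and target to outcome given treatment (b). The null is true whenever either path is zero, so a valid 5% test must hold its level for every value of the other path.

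In small samples the resampled products are skewed away from zero. The bias correction responds by moving both interval limits further from zero. If one path is truly absent and the other is sizeable, the interval then excludes zero too often.

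Both such situations are plausible here. A target such as loneliness may track binge eating in both arms without the arms differing (a = 0). Or RRT may shift a target that does not drive the outcome (b = 0), which is the result that would count against the theory. A false positive would support a mechanism that is not there and, if judged promising, would lead to the parallel process growth models that the SAP describes next.

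**Working it through.** **Inputs from the documents.** n = 60, 1:1 (Protocol A.7; SAP power section). Lower case n = 0.75 × 60 = 45, from the retention benchmark in SAP Primary Aim 1. Level 0.05, one mediator at a time (SAP).

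**Assumptions.** Two-sided test, 1,000 resamples, normal errors with unit variance, no direct effect, no covariates, no therapy-group clustering, no missing data. The SAP gives no numeric value for a medium path; 0.39 is assumed, with variants.

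**The plan's own figure.** The joint-significance test rejects when the a and b paths are each significant, so

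power = P(|t_a| > t₀.₉₇₅,ₙ₋₂) × P(|t_b| > t₀.₉₇₅,ₙ₋₃), from noncentral t.

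With a standardised treatment variable and a = b = 0.39 this gives 78.8% at 72 and 80.3% at 74. The stated 72 is therefore reproduced to within 2 patients (2/72 = 3%). The bias-corrected bootstrap, simulated in the same setting, gives 83.8% at 72 and already 81.0% at 66. The result depends on what medium means. At 72, a = b = 0.36 gives 77.7% (bias-corrected) and 68.5% (joint); a between-arm effect of 0.5 SD with b = 0.39 gives 59% and 49%.

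A note on scale: two equal arms coded ±0.5 have SD 0.5, so a path of 0.39 per SD of treatment is 0.39/0.5 = 0.78 SD between arms. On the scale that reproduces 72, the a = 0.8 rows below are roughly the plan's medium path.

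**Error when there is no indirect effect.** Data: x = ±0.5, m = a·x + e₁, y = b·m + e₂, with a·b = 0. Let z₀ = Φ⁻¹(share of resampled products below the estimate). The bias-corrected limits are the resample quantiles at Φ(2z₀ − 1.96) and Φ(2z₀ + 1.96); the percentile limits are those at 2.5% and 97.5%. Reject if the interval excludes zero. There are 4,000 trials per cell; at 8% the Monte Carlo SE is √(0.08 × 0.92/4000) = 0.4 points. Entries are rejection rates in %: BC = bias-corrected, PC = percentile, JS = joint significance.

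| a (SD) | b | BC, n=60 | PC | JS | BC, n=45 | PC | JS |
|---|---|---|---|---|---|---|---|
| 0 | 0 | 0.8 | 0.3 | 0.2 | 0.6 | 0.2 | 0.1 |
| 0 | 0.14 | 2.0 | 0.8 | 0.9 | 1.8 | 0.5 | 0.6 |
| 0 | 0.39 | 7.1 | 3.8 | 3.7 | 6.5 | 3.7 | 3.5 |
| 0 | 0.59 | 8.0 | 5.4 | 5.1 | 7.7 | 5.1 | 4.5 |
| 0.2 | 0 | 1.4 | 0.5 | 0.5 | 1.7 | 0.4 | 0.5 |
| 0.5 | 0 | 5.2 | 2.4 | 2.3 | 4.1 | 2.0 | 1.7 |
| 0.8 | 0 | 8.6 | 5.5 | 4.9 | 8.3 | 4.7 | 4.4 |
| 1.2 | 0 | 9.3 | 7.1 | 5.6 | 9.3 | 6.6 | 4.7 |

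Repeat runs at n = 60 over the inflated cells, with a largest a path of about 1.2 SD, gave bias-corrected ranges of 7.1%–8.1%, 7.3%–8.4% and 6.9%–8.7%. At a = 0.5, b = 0 they gave 5.2% to 5.7%.

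**Power given up by the percentile interval.** At a = 0.8, b = 0.39, n = 60, two runs gave 78% and 76% for bias-corrected against 69% for percentile: 78 − 69 = 9 and 76 − 69 = 7 points. At n = 72 the differences are 83.8 − 77.6 = 6.2 (a = b = 0.39), 77.7 − 68.6 = 9.1 (a = b = 0.36) and 59.3 − 49.1 = 10.2 (0.5 SD between arms, b = 0.39).

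**Number of tests.** Four targets × two outcomes × two lags = 16. If all were independent and null, the chance of at least one rejection would be 1 − 0.95¹⁶ = 56% at an exact 5%, 1 − 0.92¹⁶ = 74% at 8%, and 1 − 0.9917¹⁶ = 12% at the both-null rate of 0.83%.

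**The case against.** A reader might infer that the test runs above 5% throughout at this sample size, so that mediation will in general be declared too often. The table does not support that. With both paths absent the error is below 1%, with a small remaining path it is 2% or less, and at a = 0.5 SD it is about nominal. The documents do not say which case will apply. The SAP expects smaller effects than in the wait-list pilot because the comparator is active, which makes a large a path less likely. That part of the objection stands. It leaves the case a = 0 with b of 0.39 or more untouched, and a lower expected a path makes that case more plausible.

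A reader might also infer that the excess compounds over 16 tests. It does so only if most of them fall in the inflated cells. Multiplicity alone gives 56% at an exact 5% under independence, and a percentile interval would leave that problem in place.

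Three further points stand. The percentile interval is not exact either: it reaches 7.1% for a very large a path and is very conservative for small ones. In a pilot below its own mediation requirement (60 against 72), preferring power is a defensible choice. And little depends on the result: the Primary Aim 1 benchmarks concern recruitment, retention, attendance and satisfaction, no go/no-go rule uses mediation, and promising results lead only to exploratory models. Still, the SAP specifies a significance test and claims accuracy for it, and nothing in the plan checks either.

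**Conclusion.** The concern holds in a conditional form. At n = 60 or about 45, the stated test can reject at about 7% to 9% instead of 5% when exactly one path is null and the other is medium to large. It is conservative or near nominal elsewhere. It is therefore not a valid 5% test over the whole null, and the claim of greatest robustness and accuracy goes too far.

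The excess is at most about 4 points per test, and the SAP's fallback on effect sizes limits the harm. This is a minor improvement to the plan and no threat to the trial's main conclusions. The sizes rest on the simplified simulation model set out above; covariates, clustering or missing data could move them either way.

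**What to change.** In the SAP's mediation paragraph:

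- Make the percentile bootstrap interval the stated interval for every indirect effect, with the number of resamples and the seed fixed in advance.
- Report beside it the joint-significance test, meaning that a and b are each significant. This differs from the SAP's use of joint significance for the indirect pathways. It stays at about 5% or just above (5.6% at most in the table) even with a very large a path, where the percentile interval does not.
- Show the bias-corrected interval only as a secondary result.
- Drop or qualify the sentence on the most robust and accurate interpretation.

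The change is one option in the same software plus two regression tests already fitted, and needs no new data. The cost is the 6 to 10 points of apparent power shown above. Part of that is not a real loss, because the higher figure is bought with the inflated error. The estimated indirect effects are the same under either interval.
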